The purpose of this statistical analysis plan (SAP) is to describe in detail the planned analyses and reporting for protocol AR-15512-CS302, Amendment 2 (Rev 2) dated 04MAY2023. The statistical analysis methods presented in this document will supersede the statistical analysis methods described in the clinical protocol. If additional analyses are required to supplement the planned analyses described in this SAP, they may be completed and will be identified in the clinical study report.

This SAP is being written with due consideration of the recommendations outlined in the most recent International Conference on Harmonisation (ICH) E9 Guideline entitled Guidance for Industry: Statistical Principles for Clinical Trials¹, the most recent ICH E9 (R1) Guideline entitled Guidance for Industry: Statistical Principles for Clinical Trials: Addendum: Estimands and Sensitivity Analysis in Clinical Trials², and the most recent ICH E3 Guideline entitled Guidance for Industry: Structure and Content of Clinical Study Reports³.

2. Study Objectives

To evaluate the safety and efficacy of topical ophthalmic 0.003% AR-15512 compared to its vehicle administered twice daily (BID) in subjects with dry eye disease (DED).

2.1 Study Endpoints

[REDACTED] efficacy endpoints in [Section 2.1.1](#), [Section 2.1.2](#), and [Section 2.1.3](#) will be reported for study eye only unless otherwise specified in [Section 13.4](#), [Section 13.5](#), and [Section 13.6](#) respectively. The “Baseline” in [Section 2.1.1](#), [Section 2.1.2](#), and [Section 2.1.3](#) refers to Baseline (Day 1) visit unless otherwise specified.

2.1.1 PRIMARY ENDPOINT

- Proportion of subjects with ≥ 10 mm increase (post-drop on Day 14 vs pre-drop at Baseline) in unanesthetized Schirmer score on Day 14

2.1.2 SECONDARY ENDPOINTS

- Change from baseline in global symptom assessment in dry eye (SANDE) score on Day 28
- Change from baseline (post-drop on Day 14 vs pre-drop at Baseline) in unanesthetized Schirmer score on Day 14
- Proportion of subjects with ≥ 10 mm increase (post-drop on Day 1 vs pre-drop at Baseline) in unanesthetized Schirmer score on Day 1
- Change from baseline (post-drop on Day 1 vs pre-drop at Baseline) in unanesthetized Schirmer score on Day 1
- Proportion of subjects with ≥ 10 mm increase (post-drop on Day 90 vs pre-drop at Baseline) in unanesthetized Schirmer score on Day 90

- Change from baseline (post-drop on Day 90 vs pre-drop at Baseline) in unanesthetized Schirmer score on Day 90
- Change from baseline in global SANDE score on Day 90
- Change from baseline in SANDE frequency score on Day 90
- Change from baseline in SANDE severity score on Day 90
- Change from baseline in eye dryness score (EDS) – VAS on Day 90
- Change from baseline in ocular discomfort score (ODS) – visual analog scale (VAS) on Day 90

2.1.4 SAFETY VARIABLES

The safety variables include the following:

- Adverse events (AEs)
- Hematology, chemistry, and urinalysis
- Vital signs (heart rate and blood pressure)
- Corrected visual acuity
- Slit-lamp biomicroscopy
- Intraocular pressure (IOP)
- Dilated fundus exam

2.2 Statistical Hypotheses

The primary endpoint will be tested as follows:

H_0 : The difference between study eyes treated with AR-15512 (0.003%) and study eyes treated with vehicle, in the proportion of subjects with ≥ 10 mm increase in unanesthetized Schirmer score on Day 14 = 0.

H_1 : The difference between study eyes treated with AR-15512 (0.003%) and study eyes treated with vehicle, in the proportion of subjects with ≥ 10 mm increase in unanesthetized Schirmer score on Day 14 $\neq 0$.

2.3 Estimands

2.3.1 ESTIMAND 1 (PRIMARY ESTIMAND)

The primary comparison will be based on the ITT population targeting the treatment effect attributable to the randomly assigned treatment, regardless of compliance to study treatment and assuming subjects who discontinued due to lack of efficacy, AEs, or disallowed concurrent treatments follow the behavior of subjects in the reference arm for the duration of the study and subjects who discontinued for other reasons

(outside of lack of efficacy, AEs or use of disallowed treatment) would follow the behavior of subjects who are still in the study under same randomly assigned treatment.

[figure not shown]
- Population: subjects in the ITT population with DED defined through enrollment criteria
- Endpoint:
 - Proportion of subjects with ≥ 10 mm increase in unanesthetized Schirmer score on Day 14
- Intercurrent event:
 - Non-optimal treatment compliance is ignored. [treatment policy strategy]
 - Withdrawal due to lack of efficacy, AEs, or disallowed concurrent treatment - multiple imputations using vehicle treatment group regardless of randomized treatment group is used to impute missing data. [hypothetical strategy, missing not at random]
 - Withdrawal due to reasons other than lack of efficacy, AEs, or disallowed concurrent treatment - multiple imputations using randomized treatment is used to impute missing data. [hypothetical strategy, missing at random]
- Population-level summary:
 - Difference in the proportion of subjects with ≥ 10 mm increase in unanesthetized Schirmer score on Day 14 between AR-15512 (0.003%) and vehicle

3. Study Design and Procedures

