6.10 Participant Discontinuation/Withdrawal from the Study

A subject may exit the study by their own volition or at the discretion of the Investigator or the Medical Monitor. Any subject may decide to voluntarily withdraw from the study at any time without prejudice.

The subject may also be discontinued from the study for the following reasons:

- AEs (AEs including, in the opinion of the Investigator, clinically relevant laboratory abnormalities, and intercurrent diseases reported by the subject or observed by the Investigator with documentation on the eCRF)
- Withdrawal of Consent
- Non-compliance (e.g., non-adherence to scheduled follow-up visits or use of study intervention)

- Lost to Follow-up
- Disallowed Concurrent Treatment
- Investigator Decision
- Protocol Deviation
- Death
- Does not meet entry criteria
- Other

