4.2.2 UNMASKING

A randomization schedule for allocating the study interventions within a site will be prepared by an unmasked statistician who is not involved in the day-to-day conduct of the study.

Study intervention assignments will be masked to the Investigator, the clinical study team (Sponsor, personnel involved in day-to-day study management, Monitors, Data Managers, and Statisticians), and the subjects. Only in case of medical emergency or occurrence of AEs that warrant unmasking in the opinion of the Investigator, will the study intervention assignment(s) be unmasked and made available to the

Investigator and the Medical Monitor. In the absence of medical need, the randomization code will not be available to the above personnel until after the study is completed and the database is locked.

If the Investigator feels it is necessary to unmask a subject's study intervention assignment after an emergency situation, the Investigator should contact the Medical Monitor or designee. Only after consultation with the Medical Monitor will a decision be made as to whether or not the study intervention for the subject should be unmasked. The study intervention assignment will be revealed on a subject-by-subject basis, thus leaving the masking on the remaining subjects intact.

5. Sample Size and Power Considerations

Two hundred two (202) ITT population subjects (study eyes) per treatment group yields 99% power to conclude superiority of 0.003% AR-15512 over vehicle in the proportion of subjects with ≥ 10 mm increase in unanesthetized Schirmer score on Day 14, assuming a true difference of proportions (AR-15512 vs vehicle) of 80% vs 30% and a two-sided alpha=0.05.

Additionally, 202 ITT population subjects (study eyes) per treatment group yields 99% power to conclude superiority of 0.003% AR-15512 over vehicle in the mean change from baseline in SANDE score on Day 28 assuming a true difference (AR-15512 minus vehicle) of -7.9, a common standard deviation (SD) of 17.72, and a two-sided alpha=0.05.

Accounting for subject discontinuations, approximately 460 total subjects (230 per treatment arm) will be randomized assuming a dropout rate of 10%.

6. Data Preparation

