8.7 Multicenter Consideration

Analyses adjusting for analysis center will be conducted. Analysis centers are the same as investigative sites if the number of randomized subjects in a site is equal to or larger than 10. All investigative sites with number of randomized subjects in a site less than 10 will be pooled into an analysis center for analyses.

9. Disposition of Subjects

Disposition will be presented in terms of numbers and percentage of subjects by treatment group and for all subjects. Percentages will be calculated using number of randomized subjects as the denominator unless otherwise specified.

The number of subjects screened, screen failed, entered run-in period, and randomized will be presented. Provided that subjects may be rescreened once after initial screen failure, each subject will be reported based on his/her final enrollment status, i.e., screen failure, randomized.

The number and percentages of subjects in each analysis population (ITT, PP, and Safety) will be presented.

The number and percentages of subjects who completed the study or discontinued from the study will be presented. The reasons for study discontinuation to be summarized will include AE, withdrawal of consent, non-compliance, lost to follow-up, disallowed concurrent treatment, pregnancy, lack of efficacy, investigator decision, protocol deviation, death, and other.

The number and percentages of subjects with any protocol deviation, major deviation, minor deviation, or COVID-19 related deviation will be presented.

Subject listings, including subject disposition for randomized subjects and screen failed subjects separately, informed consent, violation of inclusion/exclusion criteria, protocol deviations, and analysis populations, will be provided. In addition, details of the study randomization, including randomization date and time, randomized treatment, actual treatment, qualifying eye, and study eye will also be included in a subject listing.

10. Demographic, Baseline Characteristics, and Other Pre-treatment Variables

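### Does the missing lack-of-efficacy reason in Protocol 6.10 push failing AR-15512 subjects into own-arm imputation?

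*SAP*

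**What the plan says.** Estimand 1 in SAP 2.3.1 has two imputation branches. The first is reference-based: "Withdrawal due to lack of efficacy, AEs, or disallowed concurrent treatment - multiple imputations using vehicle treatment group regardless of randomized treatment group". The second covers everyone else: "Withdrawal due to reasons other than lack of efficacy, AEs, or disallowed concurrent treatment - multiple imputations using randomized treatment is used to impute missing data". SAP 13.5 applies the same method to the secondary endpoints.

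Protocol 6.10 introduces its list with "The subject may also be discontinued from the study for the following reasons". Ten reasons follow, among them adverse events, consent withdrawal, disallowed concurrent treatment, investigator decision and a catch-all. Lack of efficacy is not one of them.

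SAP section 9 sets out the reasons to be tabulated for study discontinuation. That list ends with "disallowed concurrent treatment, pregnancy, lack of efficacy, investigator decision, protocol deviation, death, and other". Compared with the protocol, it adds lack of efficacy and pregnancy and leaves out failure to meet entry criteria.

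On precedence, the SAP introduction says: "The statistical analysis methods presented in this document will supersede the statistical analysis methods described in the clinical protocol".

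**The concern.** The imputation branch depends on a recorded reason, and one of the three reasons that trigger vehicle-based imputation is absent from the list in the protocol. A site working from Protocol 6.10 might record a subject who leaves because the drops do not help under consent withdrawal, investigator decision or the catch-all. SAP 2.3.1 would then impute that subject from the subject's own arm.

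Such an error would run one way. In the vehicle arm both branches draw on vehicle data, so miscoding there changes nothing. In the AR-15512 arm it swaps a vehicle-like outcome for an active-like one. The early termination visit (Protocol 7.3) includes no Schirmer, SANDE or VAS assessment, so an endpoint falling after exit rests on the imputation. The primary and secondary treatment differences could be overstated, and the conservative part of the estimand weakened.

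**Working it through.** **1. Which reasons matter for routing.**

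| Reason | Protocol 6.10 | SAP 9 | Branch in SAP 2.3.1 |
|---|---|---|---|
| Adverse event | yes | yes | vehicle |
| Disallowed concurrent treatment | yes | yes | vehicle |
| Lack of efficacy | no | yes | vehicle |
| Pregnancy | no | yes | own arm |
| Entry criteria not met | yes | no | own arm |

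Two of the three vehicle-branch triggers match. The pregnancy and entry-criteria differences do not affect imputation, because both go to the own-arm branch however they are listed. Only lack of efficacy is in question.

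**2. The plan's own figures (SAP section 5).** The inputs are "Two hundred two (202) ITT population subjects (study eyes) per treatment group yields 99% power", "assuming a true difference of proportions (AR-15512 vs vehicle) of 80% vs 30% and a two-sided alpha=0.05" for the Day 14 responder endpoint, and "assuming a true difference (AR-15512 minus vehicle) of -7.9, a common standard deviation (SD) of 17.72, and a two-sided alpha=0.05" for SANDE at Day 28.

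- Proportions: power = Φ{[Δ − 1.96·√(2p̄(1−p̄)/n)] / √[(p1(1−p1)+p2(1−p2))/n]}. With p1 = 0.80, p2 = 0.30 and n = 202, this is Φ[(0.500 − 0.097)/0.0428] = Φ(9.4), above 0.9999.
- Means: 7.9/(17.72·√(2/202)) = 7.9/1.763 = 4.48, and Φ(4.48 − 1.96) = Φ(2.52) = 0.994.

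Both agree with the stated 99%.

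**3. Effect of misrouting.** Let m be the share of the AR-15512 arm that misses the endpoint through lack of efficacy and is recorded under another reason. The documents do not give m, so it is an assumption. Correct routing gives an active-arm rate of (1−m)·0.80 + m·0.30. Misrouting gives 0.80. The overstatement is m·(0.80 − 0.30) = 0.50·m. For SANDE it is 7.9·m.

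| m | Subjects of 230 | Difference if correctly routed | Overstatement | SANDE overstatement |
|---|---|---|---|---|
| 1% | 2.3 | 49.5 points | 0.5 | 0.08 |
| 2% | 4.6 | 49.0 points | 1.0 | 0.16 |
| 5% | 11.5 | 47.5 points | 2.5 | 0.40 |
| 10% | 23 | 45.0 points | 5.0 | 0.79 |

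**4. Power with correct routing at the extreme.** At m = 10% the rates are 0.75 and 0.30. With n = 202, Φ[(0.450 − 0.097)/0.0444] = Φ(7.9), still above 0.9999. For SANDE, 7.9 − 0.79 = 7.11 and 7.11/1.763 = 4.03, so power is Φ(2.07), about 0.98.

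**5. How reachable the extreme is.** The planned 10% dropout covers all reasons up to Day 90 (Protocol 4.1: 414 of 460 complete). For the primary endpoint, m = 10% would need every active-arm dropout to leave for lack of efficacy before Day 14 and be miscoded. The effect sizes above are for Day 14 and Day 28. The documents give none for Day 90, so applying these shifts there is extrapolation.

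**6. A check that ignores the reason.** Protocol 9.4 plans a robustness analysis counting missing Day 14 responses as failures. With dropout d equal in both arms, it gives (1−d)·0.80 − (1−d)·0.30 = 0.50·(1−d), or 45.0 points at d = 10%. That equals the worst case in step 3. With dropout in the AR-15512 arm only, it gives 0.72 − 0.30 = 42.0 points, below that worst case.

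**The case for a change.** The best counter-argument is that precedence does not settle the matter. The SAP supersedes the protocol on analysis methods. It does not instruct sites, and section 9 describes a table, not data entry. If a reason was never recorded as lack of efficacy, no table can recover it. The steps that SAP 6.1 requires before final analysis include no review of withdrawal reasons. Any error would favor AR-15512.

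The direction and the limit on precedence both stand. What is missing is the link from the protocol list to the recorded code. Protocol 6.10 says why a subject may be discontinued and is not presented as a coding list. Data are entered on eCRFs (SAP 6.1), and SAP 12.1 refers to a Study Exit page whose options we cannot see. That SAP 9 both adds and drops reasons relative to the protocol fits a list taken from that page at least as well as sites coding from the protocol.

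A masked reassignment of consent, non-compliance, investigator-decision and catch-all exits would go beyond repairing a list. It would put a judgement-based reclassification into the primary estimand, which statisticians could reasonably dispute.

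Two limits apply to the mitigation. The missing-as-failure analysis is visible only in the protocol, and the SAP text around its efficacy analyses is heavily redacted, so neither its retention nor its removal can be inferred. The imputation model is not visible either. If it conditions on earlier visits, a subject doing poorly would not be imputed at the arm average, and the shifts in step 3 would be too large.

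**Conclusion.** The two lists differ, and that is a clerical slip. It does not follow that lack-of-efficacy exits are imputed from their own arm. SAP 2.3.1 defines the branch by the reason for leaving, SAP 9 carries that reason, and an analyst following the SAP routes these subjects as intended. Checking that the exit page holds the code is routine data management before lock.

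If some exits were miscoded, the assumed 50-point difference would be overstated by 0.5 points for each 1% of the AR-15512 arm affected, with an implausible ceiling of 5 points. The SANDE difference would move by 0.08 per 1%, at most 0.79. Correct routing at those ceilings would still leave power above 99.99% for the primary endpoint and about 98% for SANDE. These figures rest on the plan's own effect sizes, on an assumed miscoded share, and on imputation at the arm average. No change to the plan is warranted.

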3.1 General Study Design

This will be a Phase 3, multicenter, vehicle-controlled, double-masked, randomized study conducted at approximately 20 sites in the United States. All subjects enrolled will have DED. The study will consist of Screening (Day -14) and Baseline (Day 1) visits as well as follow-up visits on Day 7, Day 14, Day 28, and Day 90 (Study Exit). There will also be a Day 60 dispensing visit. All subjects will be exposed to the Controlled Adverse Environment (CAE®) at the Screening visit.

At the end of the Screening visit, all qualified subjects will be assigned to administer AR-15512 vehicle BID (approximately 7:00h - 10:00h and 19:00h - 22:00h) to both eyes for approximately 14 days during the vehicle run-in period. After the vehicle run-in period, subjects will be re-evaluated at the Baseline (Day 1) visit for signs and symptoms of DED. Only subjects who requalify, based on inclusion/exclusion criteria, will be enrolled in the study and randomized in a 1:1 ratio within each site to receive 0.003% AR-15512 or AR-15512 vehicle to be administered BID (approximately 7:00h - 10:00h and 19:00h - 22:00h) as 1 drop in each eye for 90 days. Efficacy will be assessed at the Baseline (Day 1) visit and Days 7, 14, 28, and 90. At the end of the Day 90 visit, subjects will exit the study. Safety assessments will be conducted at each study visit. Study design is shown in Figure 1.

Figure 1. Study Design

Scheduled study visits in Table 1 (Screening, Baseline [Day 1], Day 7, 14, 28, 60, 90/Study Exit) will be referred as such in all tables and listings to enable reviewers to understand the assessment timing without referring to the protocol visit schedule. There is no Day 0, and Day 1 is the day of randomization, on which the subjects receive their first study intervention administration. For any event (or assessment) on or after Day 1, actual study day will be calculated as, (Date of Event) – (Date of First Dose of Study Intervention) + 1. For an event before Day 1, actual study day will be calculated as, (Date of Event) – (Date of First Dose of Study Intervention).

3.2 Schedule of Visits and Procedures

The Schedule of Visits and Procedures is shown in Table 1.

Table 1 Schedule of Visits and Procedures

	Start of 2 Week Run-In (AR-15512 Vehicle)	Randomized Study Intervention Period (BID-OU, 1:1 Randomization 0.003% AR-15512: AR-15512 Vehicle)						
		Screening (Day -14)	Baseline (Day 1)	Day 7	Day 14	Day 28	Day 60	Day 90 (Study Exit)
Visit ¹	Screening (Day -14)	Baseline (Day 1)	Day 7	Day 14	Day 28	Day 60	Day 90 (Study Exit)	Early Termination
Visit Window (Days)	+3 ²	N/A	±2	±2	±2	±5	-2/+5	N/A
Informed consent	X							
Demographics	X							
Collection of used / unused study intervention		X		X	X	X	X	X
Medical, ophthalmic, and surgical history	X							
Prior or concomitant medication review	X	X	X	X	X		X	X
AE review	X	X	X	X	X		X	X
Vital signs (heart rate and blood pressure)	X	X					X	X
Urine pregnancy test (WOCBP only)	X	X					X	X
Symptom questionnaire (VAS) (Ocular Discomfort, Eye Dryness)	X	X	X	X	X		X	
SANDE questionnaire (VAS)	X	X	X	X	X		X	
Corrected visual acuity	X	X	X	X	X		X	X
Slit-lamp biomicroscopy	X	X	X	X	X		X	X

		Start of 2 Week Run-In (AR-15512 Vehicle)	Randomized Study Intervention Period (BID-OU, 1:1 Randomization 0.003% AR-15512: AR-15512 Vehicle)					
Visit ¹	Screening (Day -14)	Baseline (Day 1)	Day 7	Day 14	Day 28	Day 60 ⁶	Day 90 (Study Exit)	Early Termination
At least 10-minute rest period	X	X	X	X	X		X	
CAE exposure	X							
Inclusion and exclusion criteria	X	X						
Randomization		X						
Dispensing of study intervention ⁴	X	X		X	X	X		
At least 30 and up to 45-minute rest period		X	X	X	X		X	
Pre-drop unanesthetized Schirmer test		X	X	X	X		X	
At least 15 and up to 20-minute rest period		X	X	X	X		X	
In office administration of study intervention ⁵	X	X	X	X	X		X	
Post-drop unanesthetized Schirmer test		X	X	X	X		X	
Hematology, chemistry, and urinalysis		X					X	X
Intraocular pressure	X	X					X	X
Dilated fundus exam	X	X					X	X
Study exit							X	X

¹ All office visits must be arranged at approximately the same time of day \pm 1 hour.

² The Baseline visit should be scheduled between 11 and 14 days after the Screening visit. If absolutely necessary, the Baseline visit may be delayed up to 7 days (extending the run-in period to a maximum of 21 days).

³ Administered every 5 minutes while in the CAE.

⁴ Day 7 Randomized Intervention Kit is not to be dispensed home to the subject. A single vial is used at the Day 7 visit and then returned to the kit. The single used vial as well as remaining 4 unused vials are to be retained for accountability.

⁵ Study intervention must be removed from the refrigerator at least 30 minutes before use.

⁶ Dispensation and collection visit only.

4. Study Treatments

4.1 Method of Assigning Subjects to Treatment Groups

All subjects will be centrally assigned to randomized study intervention using interactive response technology (IRT). Before the study is initiated, the log-in information and directions for the IRT will be provided to qualified personnel at each site.

All qualified subjects will be assigned to receive AR-15512 vehicle BID to both eyes for approximately 14 days during the vehicle run-in period. Following the run-in period, all subjects who requalify at Baseline (Day 1) will be randomized in a 1:1 ratio, within each site, to receive 0.003% AR-15512 or AR-15512 vehicle. The IRT will provide the site with the specific kit number(s) for each randomized subject at the time of randomization. Sites will dispense the study intervention according to the IRT instructions and the Schedule of Visits and Assessments as in Table 1.

Individuals who do not meet the criteria for participation in this study (screen failures) may be rescreened for eligibility up to one time if there is reasonable possibility, in the Investigator's opinion, that the patient might meet the eligibility criteria. When a subject is rescreened, a new subject ID will be assigned, and the previous subject id will be recorded in the Informed Consent CRF form.

The subject ID will be in the format of xxx-xxx, with the first 3 characters being the site number and the last 3 characters sequentially numbered starting from 001 within the site, which will be used to identify subjects in all datasets and listings for this study.

